9.3.4 Demographic Data

Statistical presentation for baseline and demographic characteristics will be reported. Specifically, we will compare baseline descriptive variables between study groups using independent two-tailed t-test or Mann Whitney U test for continuous variables and Chisquare test for categorical variables, as appropriate. Similarly, individuals who complete the study protocol will be compared to those who do not. As per the latest FDA/NRC/NAS guidelines for the treatment of missing data in clinical trials, the same data will be tabulated

for patients with incomplete records. If missing outcomes are greater than 25%, multiple imputation techniques will be used as per FDA recommendations.⁸⁸

9.3.5 Study Completion

The percent of participants who complete the study, losses to follow-up, times to lost to follow-up, and reasons for discontinuation (e.g., adverse events) will be presented.

9.3.6 Final Study Analysis

The final study analysis will report the results of the above statistical analysis plan. Any additional analyses will be identified as ad hoc. A final clinical studies paper(s) will be prepared.

10 STUDY ADMINISTRATION AND ETHICAL CONSIDERATIONS

10.1 Source documents and Access to Source Data/Documents

The study site will maintain appropriate medical and research records for this study, in compliance with ICH-GCP, and institutional requirements.

In this study, CRFs will be the primary record of the patients' participation in the study, but will be supplemented by hard copy documentation of outcome assessments (e.g. completed surveys).

10.2 Ethics Approval

Submission of this protocol and the required participant-related documents (consent form, advertisements) will be made to site's REBs and/or for institutional review (if required). Written approval from the REB will be obtained in writing prior to implementation. Any changes made to the protocol and participant-related documents will be submitted for review and approval prior to implementation. Study status will be reported annually or more frequently if required. A final study notification will be forwarded at completion of the study or in the event of early termination. All serious adverse events and protocol deviations (if applicable) will be submitted for review.

10.2.1 Protocol Deviation Definitions

Protocol Deviation: The investigators and site staff will conduct the study in accordance to the protocol; no deviations from the protocol are permitted. Any change, divergence, or departure from the study design or procedures constitutes a protocol deviation. As a result of any deviation, corrective actions will be developed by the site and implemented promptly. Protocol deviations may be major or non-major.

Major Protocol Deviation (Protocol Violation): A protocol violation is a deviation from the ethics-approved protocol that may affect the participant's rights, safety, or well-being and/or the completeness, accuracy and reliability of the study data. In addition, protocol violations include willful or knowing breaches of human subject protection regulations.

Non-Major Protocol Deviation: A non-major protocol deviation is any change, divergence, or departure from the study design or procedures of a research protocol that does not have a major impact on the participant's rights, safety or well-being, or the completeness, accuracy and reliability of the study data.

10.2.2 Reporting and Managing Protocol Deviations

As per ICH GCP, the Investigator should not implement any deviation from, or changes of the protocol without prior review and documented approval/favorable opinion of the ethics committee or institutional review board of an amendment, except where necessary to eliminate an immediate hazard(s) to trial subjects, or when the change(s) involves only

logistical or administrative aspects of the trial (e.g. change in monitor(s), change of telephone number(s)). All protocol deviations (both minor and major) that have not received prior approval by the ethics committee must be reported to the ethics committee as per their applicable reporting requirements. The study coordinator will report all protocol deviations to the study PI. Where safety is involved, the DSMB will also be notified.

10.3 Informed Consent Process

Voluntary written informed consent will be obtained from all participants. A member of the site's research team (study coordinator or research nurse) will review the consent with the participant and answer questions. Participants will be given both verbal and written information that provides a detailed description of the study. Participants will be provided adequate time to consider the risks and benefits associated with their participation in the study (at least 48 hours). They will be told that participation in the study is voluntary and that he or she may withdraw from the study at any time without penalty, and the decision will not impact their standard medical care.

The procedures for conducting informed consent will be documented in the participant's study record. All participants will read, sign, and date a consent form before undergoing any study procedures. Consent materials will available in English and the information will be provided with assistance of a translator as requested. A copy of the signed consent will be given to the participant. All original signed consents will be filed in the study binder and maintained in PI's office.

The consent process will be ongoing. The consent form will be revised when important new safety information is available, the protocol is amended, and/or new information becomes available that may affect participation in the study.

10.4 Participant and Data Confidentiality

All members of the research team will respect study participants' privacy and confidentiality throughout the study. Measures will be taken to ensure that all of the data collected for this study will remain confidential in accordance with privacy legislation. Study personnel will not transmit documents, other than that previously specified, or samples containing personal health identifiers (PHI) at any time over the course of the study. Each participant will be assigned a unique code and these numbers rather than names will be used to collect, store, and report participant information. Full names and other identifying information will not be revealed unless required by law and/or for the applicable REB review, or for auditing purposes. The Subject Identification Code List that links the identity of the participant with subject ID for de-identified data will be maintained with the trial master file, according to ICH-GCP, Section 8.3. The master file will be maintained both in electronic and paper copy format. The electronic file will be encrypted and stored on a dedicated research server that only the PI and study research staff will have access to. The identity of the participants will not be revealed in any published data or in presentation of the information obtained as a result of this study. Findings will be reported in aggregate.

10.5 Data Collection and Management

Data will be submitted for every participant who is enrolled in the study, regardless of duration via paper Case Report Form or through a secured electronic data capture system (i.e. REDCap). Data available from the source documents will be either transcribed onto the paper CRF or input directly into the database (i.e. REDCap). No identifiable information will be entered.

Paper CRFs will be completed in black or blue ink only and be legible. If an entry on a CRF requires change, the correction will be made by drawing a single line through the incorrect entry, followed by entering the correct data and initialing and dating the entry. Correction fluids, markers, erasures or any form of obliteration on the CRFs will not be permitted. All fields will be completed. If data are not available, a straight line will be drawn through the applicable fields and the words "None" or "N/A" will be written. The study research assistant will be responsible for entering the data into the secure, password-protected computerized REDCap database.

Collected Participant data will be audited for completeness and accuracy by the study team every 6 months (10% of records will be audited). Queries will be generated for incomplete, unreadable and/or multiple responses to single-response entries. The Data Query Form will be given to the member of the research team for correction, clarification, and signature. Data will be amended based on receipt of the signed and returned Data Query Form. The completed Data Query Form will be retained with the original completed CRF. Data queries not returned or resolved will be coded as missing values in the database.

Additional queries may be generated following a secondary review of the entered data. Once this process has been completed, and all queries have been resolved, a third (and final) review of the database will be done in preparation for analysis. Following the final review of the database, the database will be locked for the purposes of the primary analyses. Data will be de-identified and used solely for the purposes of generating aggregate datasets for analysis of the endpoints specified in the study.

10.6 Study Records Retention

Study records will be retained for 10 years after study completion. When the archiving requirements have expired, any written records associated with this study will be destroyed using confidential shredding and the electronic database used for analysis will be deleted.

10.7 Publication and Data Sharing

Data arising from this study is the property of the Sponsoring Site, but it is the function of the Study PI to disseminate information and make it available to the public. Findings from this study will be presented at national and international scientific conferences and published in peer-reviewed journals. The identity of participants will not be revealed in

any published data or in presentation of the information obtained as a result of this study. This study is registered with ClinicalTrials.gov (NCT02259413) as per the requirement of the ICMJE.

De-identified data collected in this study may be shared with other researchers according to international guidelines (ICJME). Before publishing/sharing any data, it will be reviewed with the REB to ensure full compliance with privacy legislation.

De-identified participant data that underlie the results of study, will only be available to original study investigators, whose proposed use of data has been approved by the Study PI and an independent review committee for meta-analysis and to achieve the aims of the study. This de-identified data will be available following publication of the study results, with no end date. To gain access researchers will need to sign a data access and confidentiality agreement. All published data will be available ONLY in de-identified manner.

12 APPENDICES

Appendix 1. List of Abbreviations

Abbreviation	Definition
AE	Adverse Effect
CKD	Chronic Kidney Disease
CANN-NET	Canadian Knowledge Translation and Generation
	Network
СНІ	Centre for Healthcare Innovation
CIHR	Canadian Institutes of Health Research
CORR	Canadian Organ Replacement Registry
CNTN	Canadian Nephrology Trials Network
ECC	End Stage Kidney Disease
ESKD	End Stage Renal Disease
DSI	Dialysis Symptom Index
EQ5D-3L	EuroQol 5 Dimension – 3 Levels
EQ-VAS	EuroQol Visual Analogue Scale
HRQOL	Health-related Quality of Life
HD	Hemodialysis
ICH	International Council for Harmonisation of Technical
	Requirements for Pharmaceuticals for Human Use
	(ICH)
KFOC	Kidney Foundation of Canada
MRP	Manitoba Renal Program
NCI-CTCAE	National Cancer Institute Common Terminology
	Criteria for Adverse Events
RCT	Randomized Controlled Trial
SAE	Serious Adverse Effect
SD	Standard Deviation
WI	Wellness Institute

Appendix 2. Study Definitions

Early discontinuation	The study participant will be considered an "early discontinuation" in the event that they withdraw from the study during the initial 6 months of the study (withdrawal of consent, adverse effects etc.).
Intent-to-Treat sample	All randomized participants who receive the exercise intervention/standard-of-care
Lost to Follow-up	Study participants may be considered "lost to follow up" after the subject misses a minimum of 2 consecutive study visits, and the site personnel has made a number of unsuccessful phone contacts. The decision to early terminate the subject will be the decision of the PI, all attempts to establish contact with the subject will be documented in the study files.
Protocol Mandated Procedures	Any procedure performed solely for the purpose of this research study (not site-specific standard of care)
Randomized	A participant who has met all eligibility criteria; met with the study investigator or designee to discuss the study purpose, requirements (i.e. time requirements, schedule of events etc), discussed all the risks and benefits; signed the informed consent document and was randomly assigned to one of the two study groups.
Study Intervention	The investigational regimen and all protocol required therapies. This includes standardized lifestyle education, 26 weeks of cycling during HD and 26 weeks of home-based resistance exercises.
Terminated	A participant will be terminated prematurely from the study if: 1) Participant withdraws consent; Lost to follow-up, or; death.

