Objectives	Primary: To characterize the effect of a 12-week exercise rehabilitation program on symptom burden at 12 weeks in adults on hemodialysis (HD) Secondary: To characterize the effect of a 12-week exercise rehabilitation program on: - Symptom burden at 12, 26 and 52 weeks in adults on HD - Generic health related quality of life at 12, 26 and 52 weeks in adults on HD Tertiary: To determine the effect of a 12-week exercise rehabilitation program on: - Self-reported time required for recovery post hemodialysis at 12, 26, and 52 weeks - Physical activity behavior at 12, 26, and 52 weeks - Exercise capacity at 12, 26 and 52 weeks - Frailty status at 12, 26, and 52 weeks - Self-efficacy to exercise at 12, 26, and 52 weeks - Hospitalization rate over 1 year and hospital length of stay - Mortality at 1 year
Duration	4 years
Population	Adults on chronic in-centre hemodialysis for greater than 3 months with at least one hemodialysis-related symptom will be enrolled (n=150).
Design	Single centre randomized controlled trial with 1-to-1 parallel design, allocation concealment and assessor blinding.
Inclusion / Exclusion Criteria	Inclusion Criteria: Participants must be able to understand and provide written informed consent in English; greater than or equal to 18 years old; greater than 3 months after starting chronic HD; no expected change in dialysis modality or relocation outside of Winnipeg during intervention period (12 weeks); assessed to be safe and able to exercise by HD unit nephrologist; Exclusion Criteria: acute coronary syndrome in past 3 months; unstable arrhythmia; shortness of breath at rest or with minimal activity (NYHA Class 4); symptomatic hypoglycemia (> 2x/week in week prior to enrolment); currently participating in the MRP clinical intradialytic cycling program; score of 0 on DSI when administered at time of consent
Study Arms	Intervention arm: Standard care plus a 12 week structured rehabilitation program including lifestyle education, home-based resistance exercise and cycling during HD; n=75 Control arm: Standard care including baseline exercise counseling; n=75

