5 STUDY ENROLLMENT AND WITHDRAWAL

5.1 Participant Enrolment Inclusion Criteria

This pragmatic clinical trial is designed to evaluate a "real-world" setting, requiring a broad study population. In order to be eligible, study participants must meet the following criteria:

- 1. Adults (> 18 years old) who are > 3 months after starting chronic HD;
- 2. No expected change in dialysis modality or relocation outside of Winnipeg during the intervention period (12 weeks);
- 3. Assessed to be safe and able to exercise by the HD unit nephrologist¹;
- 4. Able to understand and provide written informed consent

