7.4 Study Groups

7.4.1 Control Arm, Standard-of-care

As recommended in clinical practice guidelines for individuals with CKD, participants will receive standardized exercise counseling at baseline.^{76, 77} Although not prohibited from participating in exercise outside of the study protocol, participants in the control group will not undergo a formal structured exercise intervention and will be asked to refrain from intradialytic cycling during the 12-week intervention period. Exercise activity will be tracked via weekly self-reported log sheets. The study kinesiologist (to control for personal trainer effect) will collect log sheets weekly during the study period. Outcome measurements will occur according to the Schedule of Events (Section 7.5).

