7.4.2 Intervention Arm, Exercise Rehabilitation Program

Participants will receive exercise counseling as per controls. To standardize intervention exercise intensity, a maximal incremental cycle test (to volitional exhaustion)⁷⁸ will be performed prior to hemodialysis on a mid-week dialysis day on an ergometer in the hemodialysis unit or at the Wellness Institute depending on availability of testing equipment and patient preference. Participants will then participate in a 12-week exercise rehabilitation program as follows (See Section 7.4.5 Study Intervention Schematic):

- 1. Standardized one-on-one lifestyle education sessions at HD provided by the study kinesiologist: Self-management exercise education using Wellness Institute Cardiac Rehabilitation program modules for 1 hr/wk during the first 4 weeks of the intervention. An additional 4 standardized sessions focused on maintenance of lifelong physical activity will be provided over the remaining intervention period.
- 2. Resistance training, using tubing and body weight, based on established guidelines:^{79, 80} Weekly resistance training education will be provided by the study kinesiologist in one-on-one format at HD during the first 4 weeks of intervention. Resistance training bands, instructions and logbooks provided for home exercise (goal 2 sessions/week) during the 26-week intervention period (See Section 7.4.6 Summary Exercise Rehabilitation Program).
- 3. Intradialytic cycling during HD (intensive and maintenance phase): Participants will cycle on TherapyCycleTM (Greely, CO) ergometers modified for dialysis beds or chairs⁸¹ with an initial target exercise intensity of 50-60% of individual maximal workload as determined by the incremental cycling test.^{49,82} Target exercise duration will be 60 minutes in the first half of each HD session, 3 times per week for 12 weeks. Rest periods will be provided as needed if participants are unable to complete 60 minutes of continuous exercise.^{82,83} Duration of total exercise time, average workload (Watts) and self-reported exercise intensity as measured by Borg Rating of Perceived Exertion (RPE) will be recorded by participants for each exercise session. Target Borg RPE will be 13, which is considered to be moderate intensity.⁸⁴ Ergometer resistance will be adjusted over time by the study kinesiologist as triggered by a 1-point change in Borg RPE.

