7.6 Prohibited Medications, Treatments, And Procedures

Participants in the control arm will be asked to refrain from intradialytic cycling during the 26-week "intervention" period. No medications, treatments or procedures will be otherwise prohibited as part of the study.

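### The plan gives both 12 and 26 weeks for home resistance, intradialytic cycling and the control-arm cycling restriction; 12 weeks is the supported length, and the 26-week statements need correcting

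*Combined protocol and SAP*

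**What the plan says.** Three elements each carry two durations in current text.

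- **Home resistance.** The synopsis (Study Arms) describes "Standard care plus a 12 week structured rehabilitation program including lifestyle education, home-based resistance exercise and cycling during HD". The opening of section 7.4.2 reads "Participants will then participate in a 12-week exercise rehabilitation program as follows", and table 7.4.6 lists 12 weeks. Item 2 of section 7.4.2, however, has "logbooks provided for home exercise (goal 2 sessions/week) during the 26-week intervention period", and then sends the reader to 7.4.6, which says 12. Appendix 2 says 26.
- **Intradialytic cycling.** Section 7.4.2 item 3 sets "3 times per week for 12 weeks" and table 7.4.6 agrees. The Appendix 2 definition of the study intervention has "26 weeks of cycling during HD and 26 weeks of home-based resistance exercises".
- **Control-arm restriction.** Section 7.4.1 asks controls to "refrain from intradialytic cycling during the 12-week intervention period". Section 7.6 asks them to "refrain from intradialytic cycling during the 26-week" period.

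Three other parts of the plan depend on the answer. Section 7.4.3 opens clinical intradialytic cycling to both arms once the intervention phase is over, where a unit offers it. Section 7.4.4 measures adherence against the number of possible sessions. Section 9.3.2 defines the on-protocol analysis of the primary outcome as 70% or more of exercise sessions in the intervention period, without giving that period a length.

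**The concern.** These statements are operative. They tell staff what to prescribe, tell controls when they may start cycling, and define what is being studied. Staff working from section 7.6 would hold controls off cycling for 14 weeks longer than staff working from section 7.4.1.

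Two analyses are exposed. The first is the week-26 comparison, which measures either persistence after the program has ended or an effect while exercise is still prescribed. Week 26 matters to this plan: section 3 includes it in the primary objective and hypothesis, the principal secondary outcome is measured then (section 4.2.2), and the Dialysis Symptom Index (DSI) analyses are repeated then (section 9.3.3). The second is the on-protocol analysis. Its outcome is measured at 12 weeks (section 4.2.1), so a 26-week denominator would classify participants partly on exercise done after the outcome was recorded.

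**Working it through.** **Which length does the text support?**

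For 12 weeks: the synopsis, the opening and item 3 of section 7.4.2, table 7.4.6 and section 7.4.1. The second inclusion criterion in section 5.1 puts the intervention period at 12 weeks. The schedule in section 7.3 names the 12-week visit as the end of intervention and the 26-week visit as a wash-out visit.

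For 26 weeks: section 7.4.2 item 2 (resistance), section 7.6 (control restriction) and Appendix 2 (both exercise types).

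Twelve weeks is much the better supported.

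**Sample size.** The plan states no total number of sessions to reproduce. Its 58 per arm (section 9.2) does reproduce: 50% versus 25%, two-sided alpha 0.05, 80% power, pooled variance and no continuity correction give 58, with power 0.802. No duration enters that calculation.

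**Planned sessions per intervention participant.** Frequencies are from table 7.4.6: cycling 3 per week, resistance 2 per week. Sessions = weeks × frequency.

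| Reading | Cycling | Resistance | Total | After week 12 |
|---|---|---|---|---|
| 12 weeks throughout | 12 × 3 = 36 | 12 × 2 = 24 | 60 | 0 |
| Section 7.4.2 as written | 12 × 3 = 36 | 26 × 2 = 52 | 88 | 14 × 2 = 28 (31.8%) |
| Appendix 2 | 26 × 3 = 78 | 26 × 2 = 52 | 130 | 14 × 5 = 70 (53.8%) |

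Goal cycling time at 60 minutes a session is 36 × 60 = 2,160 or 78 × 60 = 4,680 minutes.

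**On-protocol threshold.** Assumption: cycling and resistance are pooled into one count, which the plan does not say. Threshold = 70% of total, rounded up.

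- 12 weeks: 0.7 × 60 = 42.
- Section 7.4.2 as written: 0.7 × 88 = 61.6, so 62.
- Appendix 2: 0.7 × 130 = 91.

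Under every reading 36 + 24 = 60 sessions are scheduled by week 12. Since 60 is below both 62 and 91, perfect adherence to week 12 would not qualify on either 26-week reading.

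The reverse does not hold. With 88 sessions, 33 or fewer by week 12 already fails (33 + 28 = 61, below 62). With 130, 20 or fewer already fails (20 + 70 = 90, below 91).

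**Without pooling.** If 70% applies to each type, 26 weeks of resistance needs 0.7 × 52 = 36.4, so 37 sessions against 24 scheduled by week 12. Qualifying still needs later sessions.

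**Control restriction.** The gap is 26 − 12 = 14 weeks. Assuming controls cycle at the intervention frequency, the ceiling is 14 × 3 = 42 sessions before the week-26 visit. Uptake is not given, so the range is 0 to 42, and it arises only in units that offer the clinical program.

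**The case against.** **This is leftover wording, and 12 weeks is plain enough.** Largely right on the intended length. But the 26-week figure stands in three separate operative places, one of them the formal definition of the intervention, so correction is still needed.

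**The on-protocol harm depends on a reading the plan does not favor.** Also fair. The harm is conditional, and it concerns one supplementary analysis. It remains worth closing, because section 9.3.2 leaves the period open and section 7.4.2 item 2 attaches 26 weeks to that same term.

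**Twenty-six weeks could be an intensive phase followed by a maintenance phase.** Section 4.1 describes such a two-step intervention, and section 7.4.2 provides for kinesiologist check-ins every two weeks during maintenance, without dates. However, the cycling item names both phases and still gives 12 weeks, so maintenance may fall inside the 12. The schematic in section 7.4.5 is not in the text available here and may settle this. A reader might infer that the maintenance phase is undefined; that cannot be concluded without the figure. Nor does the six-month definition of early discontinuation in Appendix 2 help, since it concerns leaving the study.

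**Contamination is already addressed.** Section 4.2.3 includes accelerometry partly to adjust for activity among controls, and it is scheduled at week 26. This is a partial answer: section 9.3.3 specifies no such adjustment, and Appendix 5 suspended accelerometry during COVID-19.

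**Stronger readings of the conflict.** A reader might infer that controls were given contradictory orders. They were not: refraining for 26 weeks satisfies both sections, so the defect is an unclear end date. A reader might also infer that on a 26-week rule on-protocol status always turns on later sessions. Only qualifying does; some participants would already have failed by week 12.

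**Conclusion.** The inconsistency is real, and the 26-week statements are wrong as written unless the schematic shows exercise prescribed after week 12. At stake are 24 or 52 resistance sessions and 36 or 78 cycling sessions per participant, a 14-week gap in when controls may start cycling, the meaning of the week-26 comparison, and the on-protocol denominator.

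The result that nobody could qualify on-protocol without post-outcome sessions holds only if the rule is read over 26 weeks. The figures of 62 of 88 and 91 of 130 further assume pooling.

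The documents do not support extending this to the main result. The 12-week visit falls within both candidate periods, so the 12-week intention-to-treat analysis stands, as does the sample size. The documents also do not show which duration participants already treated actually followed; Appendix 5 shows only that some were on intervention. The correction should be made, but it does not threaten the primary comparison.

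**What to change.** 1. Change section 7.4.2 item 2, section 7.6 and the Appendix 2 definition of the study intervention to 12 weeks.
2. State in section 9.3.2 that the 70% rule for the 12-week outcome counts only sessions scheduled up to the 12-week visit. Say whether 70% applies to the pooled count (42 of 60) or to each type (0.7 × 36 = 25.2, so 26 of 36 cycling; 0.7 × 24 = 16.8, so 17 of 24 resistance). This is a choice for the sponsor, to be made before analysis.
3. If the schematic does show prescribed exercise after week 12, align all sections to it instead, and still limit the on-protocol count to week 12.

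Optionally, report logged exercise for weeks 13 to 26 by arm to help interpret the week-26 comparison. Logs are already collected in both arms, weekly for 12 weeks and then every two weeks for 40 (sections 7.1 and 7.7), so no new data are needed.

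The cost is a protocol amendment with ethics approval before implementation (section 10.2). The analysis of the 12-week primary comparison does not change.
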